3.2.2.1.2 Best objective response

Best objective response (BoR) is calculated based on the overall visit responses from each RECIST 1.1 assessment. (see Section 3.2.2.1.1). It is the best response a patient has had following first dose of study treatment on cycle 1, day 1; but prior to starting any subsequent cancer therapy or up to and including RECIST progression or the last evaluable assessment in the absence of RECIST progression. Categorisation of BoR will be based on RECIST 1.1 using the following response categories: CR, PR, SD, PD and NE.

The confirmation of CR or PR should be performed at the next RECIST assessment and must not be less than 4 weeks later. For determination of a best response of SD, the earliest of the dates contributing towards an overall visit assessment will be used. SD should be recorded at least 8 weeks minus 1 week (to allow for an early assessment within the assessment window), after first dose/administration of study medication at cycle 1. For CR/PR, the initial overall visit assessment which showed a response will use the latest of the dates contributing towards an overall visit assessment.

It will be determined programmatically based on RECIST using all site investigator data up until the first progression event. The denominator will be consistent with that used in the ORR analysis for the respective analysis set.

For patients whose progression event is death, BoR will be calculated based upon all evaluable RECIST assessments prior to death. For patients who die with no evaluable RECIST assessments post-baseline, if the death occurs ≤ 17 weeks (i.e., 16 weeks + 1 week to allow for a late assessment within the assessment window) after first dose/administration of study medication at cycle 1, day 1, then BoR will be assigned to the progression (PD) category. For patients who die with no evaluable RECIST assessments, if the death occurs > 17 weeks after start of treatment at cycle 1 then BoR will be assigned to the NE category.

3.2.2.1.3 Objective response rate

ORR is defined as the percentage of patients who have a confirmed visit response of CR or PR prior to any evidence of progression (as defined by RECIST 1.1 or confirmed progression by modified RECIST) and will be based on all treated patients with a baseline disease assessment and a subset of all treated patients with measurable disease at baseline separately.

A confirmed response of CR/PR means that a response of CR/PR is recorded at 1 visit and confirmed by repeat imaging not less than 4 weeks after the visit when the response was first observed with no evidence of progression between the initial and CR/PR confirmation visit. Data obtained up until

progression, or last evaluable assessment in the absence of progression, will be included in the assessment of ORR. Patients who discontinue study treatment without a RECIST progression; and receive a subsequent anti-cancer therapy (note that for this study radiotherapy is not considered a subsequent anti-cancer therapy) and then respond will not be included as responders in the ORR (i.e., both visits contributing to a response must be prior to subsequent therapy for the patient to be considered as a responder).

In the case where a patient has two non-consecutive visit responses of PR, then, as long as the time between the 2 visits of PR is greater than 4 weeks and there is no PD between the PR visits, the patient will be defined as a responder. Similarly, if a patient has visit responses of CR, NE, CR, then, as long as the time between the 2 visits of CR is greater than 4 weeks, then a best response of CR will be assigned.

A patient will be classified as a responder, if the RECIST criteria for a CR or PR are satisfied at any time following first dose/administration of study medication, prior to RECIST progression and prior to starting any subsequent cancer therapy. All responses of CR or PR must be confirmed.

Similarly, if a patient has three consecutive visit responses of CR, NE, CR, if the time between the 2 visits of CR is greater than 4 weeks, a best response of CR will be assigned.

3.2.2.1.4 Duration of response

Duration of response will be defined as the time from the date of first documented response (which is subsequently confirmed) until date of documented progression or death in the absence of disease progression (i.e., date of PFS event or censoring – date of first response + 1). The end of response should coincide with the date of progression or death from any cause used for the PFS endpoint. The time of the initial response will be defined as the latest of the dates contributing towards the first visit that was PR or CR that was subsequently confirmed.

If a patient does not progress following a response, then their duration of response will use the PFS censoring time.

3.2.2.1.5 Change in target lesion tumour size

The best percentage change in tumour size from baseline will be reported, i.e. the maximum reduction from baseline or the minimum increase from baseline in the absence of a reduction from baseline based on all post baseline assessments.

Tumour size is the sum of the longest diameters (or short axis measurements for lymph nodes) of the target lesions. Target lesions are measurable tumour lesions. Baseline for RECIST is defined to be the

last evaluable assessment prior to starting treatment. The percentage change in target lesion tumour size at each week x for which data are available will be obtained for each patient taking the difference between the sum of the target lesions at each week x and the sum of the target lesions at baseline divided by the sum of the target lesions at baseline multiplied by 100 (i.e. $(\text{week } x - \text{baseline})/\text{baseline} * 100$).

Only patients with measurable disease at baseline will be included in summaries of best percentage change in tumour size.

3.2.2.1.6 Progression Free Survival

PFS is defined as the time from first dose of Cycle 1 until the date of objective disease progression or death (by any cause in the absence of progression) regardless of whether the patient withdraws from study therapy or receives another anti-cancer therapy prior to progression (i.e. date of PFS event or censoring – date of first dose + 1). Patients who have not progressed or died at the time of analysis will be censored at the time of the latest date of assessment from their last evaluable RECIST assessment. However, if the patient progresses or dies after two or more missed visits, the patient will be censored at the time of the latest evaluable RECIST 1.1 assessment prior to the two missed visits.

If the patient has no evaluable post-baseline visits or does not have baseline data they will be censored at Day 1 unless they die within 2 visits of baseline (16 weeks plus 1 week allowing for a late assessment within the visit window).

The PFS time will always be derived based on scan/assessment dates, not visit dates.

RECIST assessments/scans contributing towards a particular visit may be performed on different dates.

The following rules will be applied:

- For investigational assessments, the date of progression will be determined based on the earliest of the dates of the component that triggered the progression
- When censoring a patient for PFS the patient will be censored at the latest of the dates contributing to a particular overall visit assessment

Note: for TLs only the latest scan date is recorded out of all scans performed at that assessment for the TLs and similarly for NTLs only the latest scan date is recorded out of all scans performed at that assessment for the NTLs.

3.2.2.2 Calculation or derivation of pharmacokinetic variables

The PK analyses of the plasma and urine concentration versus time data for AZD7648 will be performed by Covance (now Labcorp) Clinical Pharmacology Alliance, on behalf of the Sponsor and will be calculated in accordance with AstraZeneca Guidelines for PK Evaluations in Clinical Studies.

The PK parameters will be derived using non compartmental methods in Phoenix® WinNonlin® Version 8.1 or higher (Certara).

PK analysis will, where data allow, be carried out using actual elapsed times determined from the plasma PK sampling and dosing times recorded in the database. If actual elapsed times are missing, nominal times may be used. Nominal sampling times may be used for any agreed interim PK parameter calculations or graphical visualization of PK data.

The Ae will be calculated using a urine density of 1.0 g/mL. Urine concentrations below LLOQ will be treated as numerical zero.

Where data allow, the following PK parameters for AZD7648 will be derived from plasma concentrations:

Single dose Plasma PK Parameters (AZD7648 alone):
Core escalation monotherapy module, Part A, Cycle 0, Day 1**Combination escalation module, Part A, Cycle 0, Day 1**

C _{max}	Maximum observed plasma (peak) drug concentration
t _{max}	Time to reach peak or maximum observed concentration or response following drug administration
t _{last}	Time of last observed (quantifiable) concentration
AUC(0-12)	Area under the plasma concentration-time curve from time zero to 12 hours post-dose
AUC(0-24)	Area under the plasma concentration-time curve from time zero to 24 hours post-dose
AUC _{last}	Area under the plasma concentration-curve from time zero to last quantifiable concentration
AUC _{inf}	Area under plasma concentration-time curve from time zero to infinity
λ _z	Terminal elimination rate constant

$t_{1/2\lambda z}$	Half-life associated with terminal slope (λz) of a semi-logarithmic concentration-time curve, calculated as $\ln 2/\lambda z$
CL/F	Apparent total body clearance of drug from plasma after extravascular administration
<hr/>	
V_{ss}/F	Volume of distribution (apparent) at steady state following extravascular administration
V_z/F	Volume of distribution (apparent) following extravascular administration (based on terminal phase)
MRT _{inf}	Mean residence time of the unchanged drug in the systemic circulation
Dose normalised C _{max}	Maximum observed plasma (peak) drug concentration divided by the dose administered (C _{max} /D)
Dose normalised AUC _{last}	Area under the plasma concentration-time curve from time zero to time of last quantifiable concentration divided by the dose administered (AUC _{last} /D)
Dose normalised AUC _{inf}	Area under the plasma concentration-time curve from time zero to infinity divided by the dose administered (AUC _{inf} /D)
Dose normalised AUC(0-12)	Area under the plasma concentration-time curve from time zero to 12 hours post dose divided by the dose administered (AUC(0-12)/D)
<hr/>	
Single dose Plasma PK Parameters (AZD7648 in combination with anti-cancer drug PLD):	
Combination escalation module, Part A, Cycle 1, Day 1	
<hr/>	
C _{max}	Maximum observed plasma (peak) drug concentration
t _{max}	Time to reach peak or maximum observed concentration or response following drug administration
t _{last}	Time of last observed (quantifiable) concentration
AUC(0-12)	Area under the plasma concentration-time curve from time zero to 12 hours post-dose
AUC _{last}	Area under the plasma concentration-curve from time zero to last quantifiable concentration
Dose normalised C _{max}	Maximum observed plasma (peak) drug concentration divided by the dose administered (C _{max} /D)

Dose normalised AUC _{last}	Area under the plasma concentration-time curve from time zero to time of last quantifiable concentration divided by the dose administered (AUC _{last} /D)
Dose normalised AUC _{inf}	Area under the plasma concentration-time curve from time zero to infinity divided by the dose administered (AUC _{inf} /D)
Dose normalised AUC(0-12)	Area under the plasma concentration-time curve from time zero to 12 hours post dose divided by the dose administered (AUC(0-12)/D)

Multiple dose Plasma PK parameters (AZD7648 alone):

Core escalation monotherapy module, Part A, Cycle 1 Day 8 or Visit Y

AZD7648 in combination with anti-cancer drug:

Combination escalation module, Part A, Cycle 1, Day 8

C _{max}	Maximum observed plasma (peak) drug concentration
t _{max}	Time to reach peak or maximum observed concentration or response following drug administration
t _{last}	Time of last observed (quantifiable) concentration
C _{avg}	Average drug concentration over a dosing interval
C _{trough}	Lowest observed plasma (trough) drug concentration reached before the next dose is administered
AUC _τ	Area under the plasma concentration-time curve in the dosing interval τ (τ = CCI and τ = CCI)
AUC _{last}	Area under the plasma concentration-curve from time zero to last quantifiable concentration
CL/F	Apparent total body clearance of drug from plasma at steady state after extravascular administration
Dose normalised C _{max}	Maximum observed plasma (peak) drug concentration divided by the dose administered (C _{max} /D)
Dose normalised C _{trough}	Minimum observed plasma concentration divided by the dose administered (C _{trough} /D)

Dose normalised AUC _{last}	Area under the plasma concentration-time curve from time zero to time of last quantifiable analyte concentration divided by the dose administered (AUC _{last} /D)
-------------------------------------	--

Dose normalised AUC _τ	Area under plasma concentration-time curve in the dosing interval τ divided by the dose administered (AUC _τ /D)
----------------------------------	---

Rac AUC	Accumulation ratio for AUC, calculated by multiple dose AUC _τ /single dose AUC(0-12) (for CCI) or AUC(0-24) for CCI
---------	---

Rac C _{max}	Accumulation ratio for C _{max} , calculated by multiple dose C _{max} /single dose C _{max}
----------------------	--

TCP	Temporal change parameter in systemic exposure, calculated as multiple dose AUC _τ /single dose AUC _{inf}
-----	--

Single dose Plasma Diagnostic PK Parameters (AZD7648 alone):

Core escalation monotherapy module, Part A, Cycle 0, Day 1

AZD7648 in combination with anti-cancer drug:

Combination escalation module, Part A, Cycle 0, Day 1

λ_z lower	Lower (earlier) t used for λ_z determination
-------------------	--

λ_z upper	Upper (later) t used for λ_z determination
-------------------	--

$\lambda_z N$	Number of data points used for λ_z determination
---------------	--

λ_z span ratio	Time period over which λ_z was determined as ratio of $t^{1/2}\lambda_z$
------------------------	--

Rsq adj	Statistical measure of fit for the regression used for λ_z determination adjusted for the number of used data points ($\lambda_z N$)
---------	--

AUC _{extr}	Extrapolated area under the curve from t _{last} to infinity, expressed as percentage of AUC _{inf}
---------------------	---

Urine PK Parameters

Where data allow, the following parameters will be calculated for AZD7648 from the urine concentration data obtained from the Core escalation monotherapy module Part A on Cycle 0 Day 1 (CCI [REDACTED] cohorts) and Cycle 1 Day 8 (CCI [REDACTED]):

Ae(t1-t2)	Amount of unchanged drug excreted into urine from time t1 to time t2, e.g. Ae(0-8) for Cycle 0 Day 1 and Cycle 1 Day 8 (CCI [REDACTED] cohorts), Ae(8-24) for Cycle 0 Day 1 (CCI [REDACTED]) and Cycle 1 Day 8 (CCI [REDACTED]), and Ae(0-24) for Cycle 0 Day 1 (CCI [REDACTED]) and Cycle 1 Day 8 (CCI [REDACTED])
fe(t1-t2)	Percentage of dose excreted unchanged in urine from time t1 to time t2, e.g. fe(0-8) for Cycle 0 Day 1 and Cycle 1 Day 8 (CCI [REDACTED] cohorts), fe(8-24) for Cycle 0 Day 1 (CCI [REDACTED]) and Cycle 1 Day 8 (CCI [REDACTED]), and fe(0-24) for Cycle 0 Day 1 (CCI [REDACTED]) and Cycle 1 Day 8 (CCI [REDACTED])
CLR	Renal clearance of drug from plasma estimated by dividing Ae(0-24) by AUC(0-24) for Cycle 0 Day 1 (CCI [REDACTED]) and Cycle 1 Day 8 (CCI [REDACTED])

Additional PK parameters may be determined where appropriate (e.g. AUC(0-10/D) and AUC((0-24)/D)).

There will be no PK parameters determined by the PK NCA methodology for the anti-cancer agents administered in this study e.g. PLD, since only sparse PK samples were planned for collection. The concentrations for the co-administered therapies will be listed and summarised, but any PK analysis carried out on the concentrations using other methods will be reported outside the CSR for this study.

3.2.2.3 CCI [REDACTED]

The exploratory research variables are described in Section 3 of the Clinical Study Protocol.

CCI [REDACTED]
[REDACTED]
[REDACTED]

4 ANALYSIS METHODS

4.1 General principles

The below mentioned general principles will be followed throughout the study:

- The planned arm and the actual arm for each patient will be assessed by study medical monitor and provided in a separate MS Excel sheet, which will be used for study summaries. This Excel file will be filed in the TMF at the end of the study.
- Unscheduled assessments will not be included in aggregate summaries and will be listed only. The assessments which are not included in the aggregate summary will be flagged in the listing. Unscheduled assessments will be included in the patient level figures.
- Descriptive statistics will be used for all variables, as appropriate. Continuous variables will be summarised by the number of observations, mean, standard deviation, median, upper and lower quartiles (as applicable), minimum, and maximum. For log transformed data it is more appropriate to present geometric mean, coefficient of variation (CV), median, minimum and maximum. Categorical variables will be summarised by frequency counts and percentages for each category.
- Descriptive statistics will only be presented if $n \geq 3$. If no patients have data at a given time point, then only $n = 0$ will be presented. If data are available for less than 3 participants, no summary statistics other than minimum, maximum and number of observations will be presented
- Unless otherwise stated, percentages will be calculated out of the analysis set total and for modules (core, combination 1 module)/ parts (Part A: dose escalation, Part B: expansion cohorts)/doses.
- For continuous data the mean and median will be rounded to 1 additional decimal place compared to the original data. The standard deviation will be rounded to 2 additional decimal places compared to the original data. Minimum and maximum will be displayed with the same accuracy as the original data.
- For categorical data, percentages will be rounded to 1 decimal place.

- SAS® version 9.4 or higher will be used for all analyses.
- It is acceptable to present large numerical values in more appropriate units. For example, an AUC value of 123,000 ng·h/mL may be reported as 123 µg·h/mL instead of 123,000 ng·h/mL. It is, however, important to keep the units consistent within the report and the precision consistent with that prior to conversion.
- All analyses will be performed on data collected before intra-patient dose escalation, if any. Data collected after dose escalation will be presented in listings only and will be flagged. The actual dose at the time of the assessment will be presented in the listings.
- Additional sensitivity analysis might be performed on a subset of patients without important protocol deviations if needed.

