The reference date for all assessments except for tumour assessments, will be the start of the study treatment in cycle 0 (i.e., cycle 0, day 1). There is no study day 0 for this study. Date of cycle 1, day 1 dosing will be considered as the start date for the calculation of efficacy endpoints (tumour response, PFS), which follows CSP visit window starting from cycle 1, day 1. The study day will be displayed in the data listings. If an event starts before the reference start date, the study day displayed on the listing will be negative.

Time Windows

Time windows will need defining for any presentations that summarise values by visit.

Given the washout period between Cycle 0 and Cycle 1 can vary between patients (3-7 days per CSP) and therefore study day of Cycle 1 Day 1 onwards will vary, for the purposes of windowing assessments the study day of visits from Cycle 1 Day 1 onwards will be adjusted in order to allow the same window to be applied across patients. This will not impact on study day displayed in listings and will be used only by programming as an intermediate step to assign analysis visits. The amount to adjust the study day by will be derived assuming the planned day for Cycle 1 Day 1 is day 8 for all patients:

Adjustment (days) = 8 – actual Cycle 1 Day 1 study day

Study day for all safety assessments from Cycle 1 Day 1 onwards will be adjusted by this amount when assigning assessments to analysis visits. Actual, unadjusted study day will be presented in listings.

The following conventions should apply:

- Inclusion within the time window should be based on the actual date and not the intended date of the visit.
- The visit window following baseline will be constructed as per [Table 4](#) for the safety assessments
- For summaries showing the maximum or minimum values, the maximum/minimum value recorded on treatment will be used (regardless of where it falls in an interval).
- Listings should display all values contributing to a time point for a patient.
- Often the most meaningful summaries focus on extreme values rather than summaries at each visit but if summaries over time are felt to be required:
- For visit based summaries

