 - If there is more than one value per patient within a time window then the closest value to the scheduled visit date should be summarised, or the earlier, in the event the values are equidistant from the nominal visit date. The listings should highlight the value for the patient that contributed to the summary table, wherever feasible. Note: in summaries of extreme values, all post baseline values collected are used including those collected at unscheduled visits regardless of whether or not the value is closest to the scheduled visit date
- For summaries at a patient level, all values should be included, regardless of whether they appear in a corresponding visit-based summary, when deriving a patient level statistic such as a maximum.

Table 4: Visit windowing (safety analysis)

Cycle	Target Day	Analysis visit	Analysis Visit Window
	screening	Baseline	Day -28 to Cycle 0 Day 1 (pre-dose)
C0	Day 1 (pre-dose)		No analysis visit window: First day of intake of AZD7648

C0	Day 2	Cycle 0 Day 2	C0D1 + 1 day
C0	Day 3	Cycle 0 Day 3	C0D1 + 2 days
C0	Day 4	Cycle 0 Day 4	C0D1 + 3 days
C1	Day 1	Cycle 1 Day 1	No analysis visit window: Monotherapy: First day of restart of AZD7648 after C0 Combinations: Day 1 of associated anticancer agent or first day of restart of AZD7648 after C0 whichever comes first
C1	Day Y	Cycle 1 Day Y	If Y=3 then Day 2 to Day 4 If Y=7 then Day 2 to Day 7
C1	Day 8	Cycle 1 Day 8	^a Last day of previous interval + 1 day to Day 11
C1	Day 15	Cycle 1 Day 15	Day 12 to Day 18
C1	Day 22	Cycle 1 Day 22	Day 19 to C2D1 – 2 days if following cycle Otherwise Day 19 to C1D1+26 days (last cycle)
C2	Day 1	Cycle 2 Day 1	From: Monotherapy: C1D1 + 28 – 1 day or (first day of intake of AZD7648 after C1D1+28) - 1 day; if AZD7648 is off on C1D1+28-1 day. Combinations: (Day 1 of associated anticancer agent for C2 or C1D1 + 28) – 1 day; if associated anticancer agent stopped;

			
or
 
(first day of intake of associated anticancer agent after C1D1+28) – 1 day; if associated anticancer agent is off since C1D1+28-1 day
 
To:
 
Monotherapy: C1D1 + 28 + 1 day
 
or
 
(first day of intake of AZD7648 after C1D1+28) +1 day if AZD7648 is off on C1D1+28-1 day
 
Combinations: (Day 1 of associated anticancer agent for C2 or C1D1 + 28) +1 day; if associated anticancer agent stopped.
 
or
 
(first day of intake of associated anticancer agent C1D1+28) +1 day; if associated anticancer agent and off on C1D1+28-1 day.

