3.2.1.7 Laboratory Data

All laboratory results collected will be listed.

Summaries for safety laboratory will only include the parameters specified in [Table 6](#).

All values will be classified as low (below range), normal (within range), or high (above range) based on local laboratory reference ranges. Results will be converted to standard units and graded with CTCAE version 5.0. A shift table from baseline to maximum value will be summarised for urinalysis variables. Maximum post-baseline CTC grade will also be calculated.

If the same parameter is found as measured in serum and in plasma, then the summaries will not distinguish between them (e.g. values from plasma albumin and serum albumin will be summarised under albumin). If the same parameter is found as measured in serum and in plasma within the same patient, which would be a rare case, then the change from baseline will only be calculated for those post-baseline values using the same source, i.e., only within plasma or serum. If one patient has multiple toxicity grades, because they are derived separately from serum and plasma then the maximum value of the two will be considered.

For all continuous laboratory assessments, absolute value, change from baseline and percentage change from baseline will be summarised using descriptive statistics at each scheduled assessment time by actual treatment group.

For clinical chemistry and haematology, shift tables will present movements from baseline to worst value on-treatment (defined from start of treatment to biopsy day) according to reference range classification. CTCAE grade changes from baseline to on-treatment will also be provided. Corresponding shift tables (“Negative”, “Trace”, “Positive”, “0”, “+”, “++”, “+++”) will be produced for urinalysis. In addition, the number of patients with ≥ 2 CTCAE grade changes and CTCAE grade changes to 3 or 4 will be summarised by actual treatment group for clinical chemistry and haematology parameters.

Plots for both maximum post-baseline alanine transaminase (ALT) and aspartate transaminase (AST) versus the maximum post-baseline total bilirubin (expressed as multiples of their upper limit of normal [ULN] reference range) will be produced with reference lines at 3 x ULN for ALT and AST and 2 x ULN for total bilirubin. Spaghetti plots of absolute values and change from baseline values for all haematology and clinical chemistry parameters will also be presented.

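### SAP 4.1 keeps unscheduled assessments out of aggregate summaries, SAP 3.1 puts them into extreme-value summaries, and nothing says which rule governs the worst-value laboratory tables

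*SAP*

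**What the plan says.** SAP 4.1 sets out principles that apply throughout the study. One of them is: "Unscheduled assessments will not be included in aggregate summaries and will be listed only". The bullet allows one exception: "Unscheduled assessments will be included in the patient level figures".

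SAP 3.1, under Time Windows, treats by-visit and extreme-value summaries differently. For maxima and minima, "the maximum/minimum value recorded on treatment will be used (regardless of where it falls in an interval"). A note under the by-visit rule adds that "in summaries of extreme values, all post baseline values collected are used including those collected at unscheduled visits". For patient-level statistics, "all values should be included, regardless of whether they appear in a corresponding visit-based summary".

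SAP 3.2.1.7 plans outputs built on extremes:
- "Maximum post-baseline CTC grade will also be calculated".
- "A shift table from baseline to maximum value will be summarised for urinalysis variables".
- For chemistry and haematology, "shift tables will present movements from baseline to worst value on-treatment (defined from start of treatment to biopsy day").

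The same section plans counts of patients with changes of two or more CTCAE grades, or changes to Grade 3 or 4. SAP 3.2.1.11 counts patients in eight QTcF categories. The first is defined at any time on treatment; the other seven state no time basis.

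**The concern.** Safety is the primary objective, and SAP version 4.0 cut the outputs back to focus mainly on safety. The worst-value laboratory tables are therefore among the main results still to be reported, and two general-principles sections give opposite instructions for them.

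Unscheduled laboratory values are expected. Protocol 8.2.1 allows extra safety samples when clinically indicated, and Protocol 6.6 and 8.2.1 require clinically significant abnormal results to be repeated until they settle. These draws tend to happen when something is wrong, so leaving them out is not neutral.

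The adverse event tables recover such values only in part. Under Protocol 8.3.7, deterioration in a mandated test is an adverse event only if it meets serious or DLT criteria or leads to discontinuation of treatment; accompanying signs or symptoms are reported in their own right. Under Protocol 6.1.3, DLTs are assessed only in Cycles 0 and 1. A later asymptomatic, non-serious abnormality that does not stop treatment could therefore be missing from both the adverse event tables and the laboratory tables.

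**Working it through.** The plan gives no figure on this point, so the check compares the texts, establishes the direction of the effect, and reads the visit schedule.

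**1. Which outputs both rules reach**

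| Output | Extreme or any-time by its own wording? | Conflict |
|---|---|---|
| Maximum post-baseline CTC grade (3.2.1.7) | Yes | Clear |
| Chemistry and haematology shift to worst value (3.2.1.7) | Yes | Clear |
| Urinalysis shift to maximum (3.2.1.7) | Yes | Clear |
| Counts of changes of ≥2 grades, or to Grade 3/4 (3.2.1.7) | Not stated | Only if any-time is meant |
| QTcF, first category (3.2.1.11) | Yes | Clear |
| QTcF, other seven categories (3.2.1.11) | Not stated | Only if any-time is meant |

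That is three laboratory outputs and one QTcF category with a clear conflict. One further laboratory output and seven QTcF categories are conditional.

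**2. Direction of the effect**

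For one patient and one test, let S be the severities at scheduled visits and U those at unscheduled visits.
- Under 3.1 the worst value is max(S ∪ U).
- Under 4.1 it is max(S).
- Since S is contained in S ∪ U, max(S) ≤ max(S ∪ U). The two differ only when the worst unscheduled value is worse than every scheduled one.

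Following 4.1 can therefore lower an abnormal count or leave it unchanged, never raise it. If the unscheduled draw repeats an abnormal scheduled value, the first value still counts and only a worse repeat is lost.

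**3. Room for a worst value between scheduled draws**

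Inputs are the laboratory rows and footnotes b and j of Protocol Table 1 (Core Module) and Table 13 Part A (Combination Module 1), with 28-day cycles.
- Cycle 1: Days 1, 8, 15 and 22, plus Visit Y on intermittent schedules. A weekly visit may be skipped if Visit Y is within 2 days. SAP Table 4 provides for Y = 3 or Y = 7. With Y = 7 and Day 8 skipped, the longest gap is 15 − 7 = 8 days; otherwise it is 7.
- Cycle 2: Days 1 and 15, so the gaps are 15 − 1 = 14 and 29 − 15 = 14 days.
- Cycle 3 onwards: Day 1 of each cycle, a nominal gap of 28 days. The discontinuation visit and the 28-day follow-up are also scheduled laboratory visits, so a value between Day 1 visits can enter that way if treatment stops.
- Urinalysis: footnote j schedules it only at Cycle 0 and on Day 1 of each cycle, which makes the nominal gap 28 days from Cycle 1.

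**4. Weight of one patient**

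SAP 4.2 splits summaries by cohort and dose. Apart from single-patient cohorts, Part A escalation cohorts hold 3 to 6 patients (Protocol 6.1.2). One omitted patient moves a cohort percentage by 1/6 = 16.7 points at n = 6 and 1/3 = 33.3 points at n = 3. This is the effect per patient, not an estimate of how many are affected.

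**5. The analysis period**

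Three periods appear: on treatment (3.1, maximum and minimum rule), all post-baseline (3.1, extreme-value note), and start of treatment to 'biopsy day' (3.2.1.7). Protocol 8.6.3 describes an on-treatment biopsy in Cycle 1 between Day 3 and Day 8 (or Visit Y) and another on progression. The SAP does not say which is meant. Biopsies are optional outside the PD expansion cohorts and the PD subgroup of an efficacy expansion cohort (Protocol 8.6.3; Table 1, footnote l), so many patients may have neither.

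**The case against.** The best reply is that the sections can be harmonised. SAP 3.1 is the more specific rule: it separates by-visit from extreme-value summaries and names unscheduled visits only for the latter. SAP 4.1 is generic, and its next sentence, on flagging omitted assessments in listings, resembles the by-visit listing rule in 3.1. Output specifications are held in a separate document and outputs follow sponsor standards; neither was available here, and either might settle the matter.

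This is probably the intent, but it is not the text. Section 4.1 applies throughout the study, says listed only, and allows a single exception that is not extreme-value tables. A programmer following it would be following the SAP.

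Several limits on the consequence stand:
- Listings and patient-level figures keep every value.
- The Safety Review Committee reviews all available safety information (Protocol 6.1.4).
- Potential Hy's Law cases from any laboratory source, including draws outside study visits, are reported as serious adverse events (Protocol Appendix E).
- Marked liver elevations are tabulated and plotted over time (SAP 3.2.1.7).
- Data after intra-patient dose escalation are listed only under either rule (SAP 4.1).

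A reader might also infer that all eight QTcF categories are in conflict. The documents do not support that: seven state no time basis, and if they are by-visit counts no conflict arises. The one repeat ECG requirement found in the protocol is confirmation of QTc prolongation in the DLT definition, so a large volume of unscheduled ECGs cannot be assumed either.

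**Conclusion.** The contradiction is real and unresolved in the SAP. It clearly covers three worst-value laboratory outputs and one QTcF category; it extends to the grade-change counts and the other seven QTcF categories only if they are any-time summaries. Read literally, 4.1 biases these tables one way, towards fewer abnormal patients. The number affected cannot be derived, because the documents do not say how many worst values fall on unscheduled draws. The effect is on the reported tables, not on dose decisions or the underlying record.

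The 'biopsy day' cut-off is a separate defect in the same outputs. It is tempting to conclude that the shift tables stop at Cycle 1 Day 3 to 8. That follows only if the on-treatment biopsy is meant, and a progression biopsy is equally possible on the text. What is certain is that the end date is undefined and that many patients may have none.

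Nor do the documents show whether maximum CTC grade should be limited to on-treatment values: 3.1 points both ways, and the sponsor has to choose.

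**What to change.** 1. Amend the sentence in SAP 4.1 to: *Unscheduled assessments are excluded from by-visit summaries only; extreme-value summaries (maximum CTC grade, worst-value and maximum-value shifts, and any-time category counts) include them per Section 3.1.*
2. Cross-refer to this rule in SAP 3.2.1.7 and 3.2.1.11.
3. State the time basis of the grade-change counts and of each QTcF category.
4. Reconcile the on-treatment and all-post-baseline wordings in SAP 3.1 into one stated analysis period.
5. In SAP 3.2.1.7, replace 'biopsy day' with an end date that every patient has.

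The cost is a few sentences of SAP text and a check that the output specifications agree. No new data, visits or patients are needed.
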